#### C.4.9.3 6 Months

The following assessments will be conducted at the 6 Month visit.

- Physical examination
  - Vital signs
  - Major system findings
- NYHA classification
- Concomitant Medications
  - Use of relevant medications (diuretics, aspirin, anticoagulants, ACE-I, ARB, beta-blockers, statins and anti-platelets)
- Abbreviated Neurological Assessment
  - National Institute of Health Stroke Scale (NIHSS)
- Transthoracic Echocardiogram (TTE)
- 12-lead Electrocardiogram
- Quality of Life Questionnaires
- Adverse Event Review

#### C.4.9.4 12 Months

The following assessments will be conducted at the 12 Month visit.

- Physical examination
  - Vital signs
  - Major system findings
- NYHA classification
- Concomitant Medications
  - Use of relevant medications (diuretics, aspirin, anticoagulants, ACE-I, ARB, beta-blockers, statins and anti-platelets)
- Neurological Assessments
  - National Institute of Health Stroke Scale (NIHSS)
  - Modified Rankin Score (mRS)
  - Mini-Mental State Exam (MMSE-2:SV)
  - Additional Neurological testing:
    - Visual Fields Testing
    - Gait Assessment
    - Hand Function
    - Writing Evaluation
    - Drawing Assessment
- Transthoracic Echocardiogram (TTE)
- 12-lead Electrocardiogram
- 6 Minute Walk Test
- Quality of Life Questionnaires
- Adverse Event review

#### C.4.9.5 18 Months

The following assessments will be conducted at the 18 Month visit.

- Physical examination
  - Vital signs
  - Major system findings
- NYHA classification
- Concomitant Medications
  - Use of relevant medications (diuretics, aspirin, anticoagulants, ACE-I, ARB, beta-blockers, statins and anti-platelets)
- Abbreviated Neurological Assessment
  - National Institute of Health Stroke Scale (NIHSS)
- 12-lead Electrocardiogram
- Quality of Life Questionnaires
- Adverse Event review

#### C.4.9.6 24 Months

The following assessments will be conducted at the 24 Month visit.

- Physical examination
  - Vital signs
  - Major system findings
- NYHA classification
- Concomitant medications
  - Use of relevant medications (diuretics, aspirin, anticoagulants, ACE-I, ARB, beta-blockers, statins and anti-platelets)
- Neurological Assessments
  - National Institute of Health Stroke Scale (NIHSS)
  - Modified Rankin Score (mRS)
  - Mini-Mental State Exam (MMSE-2:SV)
  - Additional Neurological testing:
    - Visual Fields Testing
    - Gait Assessment
    - Hand Function
    - Writing Evaluation
    - Drawing Assessment
- Transthoracic Echocardiogram (TTE)
- 12-lead Electrocardiogram
- 6 Minute Walk Test
- Quality of Life Questionnaires
- Adverse Event review

#### C.4.9.7 3-5 Years

The following assessments will be conducted at the 3, 4, and 5 year visits.

- Physical examination
  - Vital signs
  - Major system findings
- NYHA classification
- Abbreviated Neurological Assessment
  - National Institute of Health Stroke Scale (NIHSS)
- Transthoracic Echocardiogram (TTE)
- 12-lead Electrocardiogram
- Quality of Life Questionnaires
- Adverse Event review – refer to C.5.2 Reporting for AE reporting requirements post-24 Months

#### C.4.10 Echo Assessment

Echocardiography is the cornerstone of baseline and follow-up imaging. A comprehensive transthoracic echocardiogram (TTE) to assess the morphology and function of the respective heart chambers and valves is mandatory prior to implant. Calculation of LVEF by visual assessment, measurement of left ventricular end-diastolic volume and diameter and inter-ventricular septal thickness to characterize the left ventricle and transaortic jet velocity, mean transaortic gradient and aortic valve area by the continuity equation to illustrate AS severity are essential(1).

Echo assessment will be conducted by a core laboratory.

Sites should make every effort to utilize the same echo machine for all subjects at all required interval throughout the duration of the protocol.

#### C.4.11 Neurologic Assessment

The incidence of new clinically detectable neurological events or deficits, or any comparative change in indices of higher cognitive function following TAVI in the treatment of patients with symptomatic severe aortic stenosis is an important clinical endpoint. Therefore, a baseline and follow-up neurological examination by a qualified trial-trained neurologist or stroke specialist is mandatory and as outlined in section C.4.9 Follow-Up Evaluations. Abbreviated Neurological Assessments, requiring completion of only the NIHSS, may be conducted by certified site personnel.

**If at any time there is change in a subject's NIHSS score of  $\geq 4$  further assessments should be conducted to identify potential adverse events and additional neurological evaluations should be conducted by a neurologist or stroke specialist, if a neurological event is suspected.**

In case of a new neurological event, the diagnosis of stroke should be supported by complementary findings on neuro-imaging examination. The need for additional imaging is up to discretion of the Neurologist or Stroke Physician. Both diffusion-weighted Magnetic Resonance imaging and multi-slice Computed Tomography are valid neuro-imaging modalities (however CTA or MRA is preferred to CT or MRI), the selection of which will be left per institution's standard of care.

In addition to the neurological assessments at specified time periods, additional evaluations should be conducted, as follows during the course of the trial, if applicable:

- NIHSS:
  - For subjects with a new neurological event (stroke, TIA, or encephalopathy), additional NIHSS exams are to be performed at 30 days, and 3 months post-event
  - NIHSS also to be done within 24 hours of any aortic valve or ascending aortic intervention
    - Any patient with evidence of a new neurological event should have a neurology consult and an imaging study if deemed necessary
    - *NIHSS may be conducted by certified site personnel*
- Modified Rankin Scale
  - For subjects with new neurological event, assessment to be performed at 7 days or discharge (whichever occurs first), 30 days, and 3 months post-stroke
    - *All trial-required mRS testing should be conducted by a neurologist or stroke specialist*
- Mini Mental State Exam (MMSE-2:SV)
  - For subjects with a new neurological event assessments are to be performed at 30 days and 3 months post-stroke
    - *All trial-required MMSE testing should be conducted by a neurologist or stroke specialist*

Refer to the **Appendix R.18** for a description of the Additional Neurological Testing.

#### *C.4.12 Angiographic and Computed Tomography Assessment*

Complete angiographic (invasive or MSCT) assessment of the aortic bifurcation and ilio-femoral-arterial tree is mandatory prior to the Heart Team review.

An additional benefit of Multislice CT scan in the TAVI cohort is to obtain a thorough assessment of the anatomy of the left ventricular outflow tract (LVOT) up to the common femoral arteries. MSCT also provides information on coronary and carotid anatomy, and might identify occult malignancy which is also valuable information in SAVR cohort.

The aortic valve calcification should be evaluated to determine grade of severity. With respect to the elliptical shape of the virtual aortic annulus, the axial plane where the 3 basal aortic leaflet attachments can be identified simultaneously is used for measuring the maximum and minimum annular diameter (most often corresponding to 2 orthogonal sagittal and coronal planes)(53). Additionally the maximum diameters of the LVOT, sinuses of Valsalva and sinotubular junction are obtained. Maximum diameter, calcification and tortuosity of the ascending and descending thoracic aorta are evaluated. As for the iliofemoral tree, the minimal luminal diameter, plaque and calcification burden and tortuosity are assessed in order to judge transfemoral accessibility for the investigational TAVI device.

**C.4.13 Data Collection**

All scheduled testing and procedures to be conducted during the baseline, index procedure, and follow-up assessments are summarized in **Table 3**.

**Table 3: Schedule of Assessments**

Parameter	Screening	RANDOMIZATION	Baseline	Procedure	Discharge	30 days	3 Months	6 Months	12 Months	18 Months	24 Months	3 – 5 years
			(within 14 days of procedure)									
Informed consent (and in US HIPAA Authorization)	•											
Inclusion/Exclusion	•			•*								
Demographics and Medical history	•											
Physical Examination	•		•		•	•		•	•	•	•	•
Clinical Assessments	•											
NYHA Class	•		•			•		•	•	•	•	•
Risk Assessments: STS Risk Score, Logistic EuroSCORE, EuroSCORE II, SYNTAX Score, and Katz Index	•											
Co-morbidities	•											
Concomitant Medications 			•	•	•	•		•	•	•	•	
Routine Laboratory Tests	•		•	• 	•	• 						
Neurological Assessments  (NIHSS, mRS, MMSE-2:SV and Additional Neurological Assessments) 			•		•				•		•	
Abbreviated Neurological Assessment (NIHSS only)				• 		•		•		•		•
Transthoracic Echocardiogram (TTE)	•			• 				•	•		•	•
Computed Tomography (CT) Angiogram (MSCT required at screening) 	•											
Coronary Arteriogram	•			(•)								
Aortogram				(•)								
12-lead Electrocardiogram	•		•	• 	•	•		•	•	•	•	•
6 Minute Walk Test			•			•			•		•	
Quality of Life Questionnaires (EQ-5D, KCCQ, and SF-36)			• 			•	• 	•	•	•	•	•
Adverse Events			•	•	•	•		•	•	•	•	• 

- \* Document any changes to subject condition that affect inclusion/exclusion criteria, confirm the subject does not meet any exclusion criteria specific to the Index Procedure (eg. percutaneous coronary or peripheral intervention and evidence of an acute myocardial infarction which must not occur within 30 days prior to the index procedure)
- (•) TAVI subjects only (SAVR subjects will not have these assessments)
  -  Laboratory test results must be performed pre-procedure and CK to be obtained within 8-12 hours post-procedure
  -  Pre-procedure
  -  Only hemoglobin, creatinine and creatinine clearance are required to be collected
  -  Electrocardiogram within 48 hours post-procedure
  -  TTE to be completed at least 24hours post-procedure but prior to discharge (and no later than 7 days post procedure) to assess device success
  -  All subjects should have screening thoracic and abdominal CT angiograms with complete visualization of both iliacs, femorals, and aorta (and subclavian/axillaries, if applicable), up to and including the aortic annulus
  -  In addition to the protocol required assessment (NIHSS and MMSE); for subjects with neurological event or stroke, additional NIHSS and MMSE exams are to be performed at 30 days and 90 days post-event. mRS should be completed at 7 days post-event or discharge (whichever occurs first), 30 days, and 90 days post-event. NIHSS is also to be done within 24 hours of any aortic valve or ascending aortic intervention
  -  NIHSS to be done within 24 hours post- procedure
  -  Additional Neurological Assessments include: Visual Fields Testing, Gait Assessment, Hand Function, Writing Evaluation, and Drawing Assessment
  -  SAE, MAE, cardiovascular events, device-related events, including device-related technical observations, UADEs, USADEs, all stroke (CVAs), and death reports
  -  Use of relevant medications (diuretics, aspirin, anticoagulants, ACE-I, ARB, beta-blockers, statins and anti-platelets)
  -  Quality of Life Questionnaires collected at baseline may be administered any time after the subject has provided informed consent but should be collected prior to informing the subject of randomization assignment
  -  Quality of Life Questionnaire – EQ-5D to be administered via telephone. SF-36 will also be collected in selected geographies, refer to **Appendix R.12**

#### *C.4.14 Unscheduled Follow-up Assessments*

If a subject returns to the institution between their scheduled follow-up visits the visit will be treated as an unscheduled visit and the assessments completed at this visit will be done at the discretion of the investigator. eCRFs are provided for unscheduled visits.

#### *C.4.15 Missed Follow-up Visits*

Every effort should be made to ensure subjects return to the clinic for all protocol required follow-up. If the subject is unable to return for an in-person clinic visit, the Investigator, or designee, must document in the patient record the reason the subject was unable to complete the visit and, if applicable, follow the requirements for deviation reporting as outlined in Section C.4.18 Protocol Deviations.

The Investigator should also make every effort to contact the subject or subject's legal representative, within the visit window, to collect the subject's vital status as well as information related to potential adverse events, safety data, and hospitalizations.

#### *C.4.16 Investigational Product Accountability*

The Investigator is responsible for maintenance of the Device Accountability Log. The log must detail the product and lot numbers as well as the location and status of all investigational devices (including DCS,CLS/ LS components, where applicable) received by the hospital and/or Investigator. At the end of the clinical trial the Principal Investigator must sign the original log, as applicable.

This clinical trial will be conducted in some geographies where the TAV device or its components are commercially available. In these geographies, the device will be used outside the current approved indication; therefore the TAV will be labeled as investigational. Note, the DCS and CLS/LS components are identical to the CE marked CoreValve System and will be supplied within the approved commercial CE marked labeling. The Investigator must provide full accountability for each TAV from the time of receipt through disposition and/or return. Accountability for the each DCS and CLS/LS must include all dispositions within the clinical trial. In the US, commercially labeled devices may be used in the trial, as necessary in the event that the investigational device is not available. All commercial components must have full accountability for each component from the time of receipt through disposition and/or trial. In the event that a commercial device is used in a study subject, the device use will be documented in the Device Accountability Log.

In geographies where the device is not currently approved, the TAV, DCS, CLS/LS components will be labeled as investigational. The Investigator must provide full accountability for each TAV, DCS, and CLS/LS from the time of receipt through disposition.

At the end of the trial enrollment period, all remaining investigational product must be returned to Medtronic.

#### *C.4.17 Device Malfunction or Explant*

In the event of a device malfunction of the TAV device or its components prior to implant or in the event that a TAV is explanted after implant (due to reintervention or autopsy), the TAV and/or affected components should be returned to Medtronic to the following:

Medtronic, Inc.  
Attn: Explant Lab [PE#]  
[name]  
[name]

Additional details surrounding the device return process, including how to obtain the PE # (product experience number), are contained within the Medtronic explant kit and in **Appendix R.11**.

#### C.4.18 Protocol Deviations

A protocol deviation is defined as an event where the clinical investigator or site personnel did not conduct the trial according to the protocol or the Investigator agreement. Deviations will be reported regardless of whether medically justifiable, pre-approved by Medtronic, or taken to protect the patient in an emergency.

A protocol deviation form is to be completed for each trial protocol deviation, including, but not limited to:

- Failure to obtain informed consent
- Incorrect version of consent provided to patient
- Failure to obtain IRB/MEC protocol review and approval before starting the trial
- Enrollment of patient during an IRB/MEC approval lapse
- Clinical investigator exceeding enrollment limits specified by sponsor
- Patient did not meet inclusion/exclusion criteria
- Incorrectly performed testing
- Protocol-required testing and/or measurements not done or performed outside of window
- Source data permanently missing
- SAE, SADE, UADE or USADE not reported in the required timeframe

FDA regulations [21 CFR 812.140] require that the Investigator maintain accurate, complete, and current records, including documents showing the dates of and reasons for each deviation from the protocol. Relevant information for each deviation will be documented on a deviation form completed by site personnel and reviewed by the Investigator.

FDA regulations [21 CFR 812.150], ISO 14155 (2011), and local regulatory authorities (where applicable), require Investigators to obtain prior approval from the sponsor before initiating changes in or deviations from the protocol, except when necessary to protect the life or physical well-being of a patient in an emergency.

Prior approval by the sponsor is expected in those situations in which the Investigator anticipates, contemplates or makes a conscious decision to depart from procedures specified in the protocol. Prior approval is generally not expected in situations where unforeseen circumstances are beyond the Investigator's control, but is still considered a deviation (eg. a trial subject who fails to attend a scheduled follow-up visit, a trial subject too ill to perform a protocol-required test). To obtain approval, the Investigator must call or email and discuss the potential deviation with the Medtronic trial manager or designee prior to initiating any changes. If approval is granted, the Medtronic trial manager or designee will provide the applicable documentation to be maintained in the site files.

FDA regulations require the Investigator to notify the sponsor and the reviewing IRB/MEC within 5 working days of the following deviations [21 CFR 812.150]:

- a deviation from protocol to protect the life or physical wellbeing of a patient in an emergency
- failure to obtain an informed consent

Investigators or an authorized designee must notify Medtronic as soon as possible by calling the trial manager or designee and completing the protocol deviation form.

The Investigator is required to adhere to local IRB/MEC procedures for reporting deviations.

The DSMB may review protocol deviations to ensure compliance and overall trial integrity.

#### *C.4.19 Subject Withdrawal or Discontinuation*

All subjects will be encouraged to remain in the trial through the last follow-up visit at month 60. Subjects who discontinue participation prematurely after randomization will be included in the analysis of results (as appropriate) but they will not be replaced in the enrollment of total trial subjects. If a trial subject is discontinued from the trial early, the reason for discontinuation should be documented in the patient file and a Study Exit eCRF must be completed. If discontinuation is because of safety concerns or lack of effectiveness, the subject shall be asked to be followed for collection of ongoing safety data outside the clinical investigation.

The trial site and Sponsor will make every effort to have all subjects complete the follow up visit schedule. A subject will not be considered lost-to-follow-up unless all efforts to obtain compliance are unsuccessful. At a minimum, the effort to obtain follow-up information must include three attempts to make contact via telephone and if contact via phone is not successful, a traceable letter from the Investigator must be sent to the subject's last known address. Should both telephone and mail efforts to contact the subject be unsuccessful, the subject's primary physician should be contacted. Subjects will then be deemed lost to follow up. All contact efforts to obtain follow-up must be documented in both the subject's medical records and in the trial eCRFs.

If a subject officially withdraws from the trial but is willing to allow either regular vital status determinations for the trial or a one-time vital status determination, these are to be conducted per the follow-up visit schedule or only at the last planned follow-up visit, respectively, and may be conducted via telephone.

If a subject discontinues the trial at any time, is withdrawn from the trial early, or completes all protocol required follow-up they should then be followed per the local standard of care for their condition.

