### R.24.1 SURTAVI Risk Model Rationale

#### 1. Joint database

Following the initial report by the Bern, Rotterdam collaboration (28) including 1122 patients with severe AS, four academic institutions in Bern, Rotterdam, Bad Nauheim and Munich have created a joint database on all consecutive patients with severe AS treated with either TAVI or SAVR between January 2006 and December 2009.

Preliminary analysis on 3688 patients has been performed, including 789 TAVI and 2899 SAVR patients.

The pre-specified primary outcome was all cause mortality at 1 year. Patients were actively followed up after the index procedure and their vital status confirmed by outpatient clinic visit, telephone contact, review of medical records or national civil registries.

[figure not shown]

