#### Sample Size Justification

The assumed values  $\pi_T = \pi_C = 0.17$  are based on the data published by Iturra et al and CoreValve US Pivotal High Risk study results. As reported in the Iturra paper, the incidence of all-cause mortality at 30 days was 2.8% and the late all-cause mortality Kaplan-Meier rate at 24 months was 12.1%. The overall 24-month all-cause mortality rate was approximately 15%. STS score reported in the Iturra paper ( $5.6 \pm 1.1$ , n=502) was similar to the STS score for subjects currently enrolled in the SURTAVI study ( $5.6 \pm 1.4$ , n=654), and it is believed that the 24-month all-cause mortality rate in SURTAVI will be approximately 15% at 24 months. The major stroke rate was 3.2% for subjects who survived to 1 year in the CoreValve Pivotal High Risk study. The High Risk study enrolled a higher-risk population than SURTAVI, therefore, the major stroke rate in the High Risk study is adjusted downward, and it is believed the disabling stroke rate at 24 months would be approximately 2% in the SURTAVI study. Overall, the estimation of the all-cause mortality or disabling stroke rate at 24 months is 17%.

Although the pre-specified analysis methods are Bayesian, the sample size is guided by a standard frequentist non-inferiority power analysis. Under the assumptions of  $\pi_T = \pi_C = 0.17$ , non-inferiority margin  $\delta=0.07$ , 1:1 randomization,  $\alpha= 0.05$ , and power = 95%, the method of Farrington and Manning as implemented in PASS 2008 indicates that the required sample size for a single-look analysis is 1258. To allow for up to 6% dropout, 1339 subjects must be accrued. Furthermore, to compensate for power lost in a two-look group sequential analysis plan using Pocock-type alpha spending, the sample size would have to be increased by about 12.5%. This leads to an estimated sample size of 1531. Thus a sample size of 1600 mITT subjects should provide ample power for establishing non-inferiority in the primary hypothesis test.

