#### *C.6.6 Missing Data and Planned Sensitivity Analyses (Primary Objective)*

Every effort will be undertaken to minimize missing data. However, some missing data is inevitable, and the trial is designed with the expectation that there may be up to 6% of primary data missing at 24 months. The reasons for missing data will be described in detail and evaluated for assessment of possible bias. The distribution of prognostic factors between patients with data and those without data will be examined to evaluate any potential sources of bias.

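### The minimum tracing steps require neither a death-registry search nor a vital-status sweep of lost and withdrawn subjects before the 24-month analysis

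*Combined protocol and SAP*

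**What the plan says.** Section C.4.19 of the protocol gives the rule for declaring a subject lost. The effort "must include three attempts to make contact via telephone". If these fail, "a traceable letter from the Investigator must be sent to the subject's last known address". If that fails too, "the subject's primary physician should be contacted. Subjects will then be deemed lost to follow up". The section presents these steps as a minimum and adds a general condition: "A subject will not be considered lost-to-follow-up unless all efforts to obtain compliance are unsuccessful".

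The same section covers subjects who formally withdraw but still allow vital-status checks. Those who accept regular checks are followed on the visit schedule, which includes month 24. Those who accept only one check have it at the last planned visit, and the section puts that visit at month 60.

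Section C.4.15 covers missed visits. The investigator should "make every effort to contact the subject or subject's legal representative, within the visit window, to collect the subject's vital status". The 24-month visit has a window of 730 ± 60 days (C.4.9).

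C.6.6 accepts that "the trial is designed with the expectation that there may be up to 6% of primary data missing at 24 months". It asks for the reasons to be described and for prognostic factors to be compared between subjects with and without data. Its heading announces sensitivity analyses, but the text names none. C.6.5.2 refers further analysis detail to the SAP.

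Registries appear only in Appendix R.24.1. There the background risk-model cohort had vital status confirmed by several routes, among them "review of medical records or national civil registries".

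**The concern.** The primary endpoint is all-cause death or disabling stroke at 24 months, and most of it is death. Death is the one component that can often be established without the subject's cooperation. Yet every required tracing step depends on a person answering: the subject, a legal representative or a physician. A subject who has moved or died may yield nothing by these routes and still be traceable in public records.

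The one-time check is a separate problem of timing. It yields consented mortality information, but too late for the analysis that needs it.

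The comparison is open label, between surgery and a catheter procedure. Loss to follow-up, or the risk among those lost, could differ between the arms. If it does, unfound deaths bias the difference in rates. Unfound events mainly in the TAVI arm would make non-inferiority easier to declare; mainly in the SAVR arm, harder.

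**Working it through.** **Inputs.** From C.6.5.1 and C.6.5.2: mortality ("24-month all-cause mortality rate in SURTAVI will be approximately 15" percent), disabling stroke 2%, composite 17% in both arms, margin 7 points, alpha 0.05, power 95%, 1:1 allocation, 1600 mITT subjects, Beta(1,1) priors, posterior threshold 0.971. From C.6.6: up to 6% missing. Event rates among missing subjects, and missing shares by arm, are not in the documents and are assumptions below.

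**The plan's own figures.** With the Farrington–Manning formula, the null-restricted rates are 0.2105 and 0.1405.

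- V0 = 0.2105 × 0.7895 + 0.1405 × 0.8595 = 0.287
- V1 = 2 × 0.17 × 0.83 = 0.282
- n per arm = [1.645 × (√V0 + √V1) / 0.07]² = 628.6, so 629 per arm and 1258 in total, as stated
- 1258 / 0.94 = 1338.3, so 1339, as stated
- 1339 / (1 − 0.125) = 1530.3, so 1531, as stated

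The calculation is sound. With 1504 evaluable subjects (94% of 1600), approximate single-look power is 97.6% at one-sided 0.05 and 95.7% at 0.029 (that is, 1 − 0.971). The issue is therefore bias, not power.

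**Share of the endpoint that is death.** 15 / 17 = 88%.

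**Number affected.** 0.06 × 1600 = 96 subjects, 48 per arm, if the allowance is fully used. Assumed mortality of 10, 15, 30 or 45% among them gives about 10, 14, 29 or 43 deaths. These are upper bounds on what a search could find: not every missing outcome is a lost subject, and not every death is in a registry.

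**Timing of the one-time check.** Enrollment is planned over about 36 months (C.3.5), so the last subject reaches month 24 about 36 + 24 = 60 months after the first was enrolled. Only the very earliest subjects reach their month-60 visit by then. The interim Win Look, when 1400 subjects have reached 12 months, comes earlier still.

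**Shift in the difference.** If the observed rate is 17%, a fraction m of an arm is missing, and the event risk among the missing is q, that arm's true rate differs from the observed one by m × (q − 0.17).

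- 6% missing per arm; q = 25% in one arm, 17% in the other: 0.06 × 0.08 = 0.5 points
- Same, q = 35% against 17%: 0.06 × 0.18 = 1.1 points
- 6% missing per arm, q equal in both: 0 points
- 4% missing in one arm, 8% in the other, q = 34% in both: (0.08 − 0.04) × 0.17 = 0.7 points

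**Against the room available.** A simulation of the Beta(1,1) posterior at threshold 0.971, with 752 observed per arm and 128 SAVR events, loses non-inferiority from 153 TAVI events, a difference of 25 / 752 = 3.3 points. A shift of 0.5 to 1.1 points is roughly a seventh to a third of that. With equal observed rates (128 events each) and 8 events among the 48 missing SAVR subjects, non-inferiority is lost only if at least 35 of the 48 missing TAVI subjects (73%) had events. With no events among the missing SAVR subjects, the figure is 28 of 48 (58%).

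**The case against.** Four points on the other side have force.

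- **The steps are a floor.** C.4.19 calls them a minimum and adds the condition that all efforts must have failed. A registry search is not required, but it is not excluded either. This stands.
- **Contact at 24 months is not absent.** A reader might infer that a subject lost at month 6 is never checked again. The documents do not say so. C.4.15 asks for vital-status contact in each missed visit window, and withdrawn subjects may accept checks on the visit schedule. What remains is silence on whether C.4.15 applies once a subject has been deemed lost.
- **The handling of missing primary outcomes is not visible.** A reader might infer that lost subjects are predicted at the average 17%. Sections C.6.5 and C.6.6 do not say this; the wording about predictions is attached to secondary endpoints in C.6.8. The text reviewed here is part 3 of 4, does not contain the SAP, and has the consent pages removed. A registry provision or a missing-data rule may be in those pages.
- **The size is a scenario.** The 25 to 35% risk has no source in the documents and is applied to one arm only. The 6% covers all missing primary data, not only losses to follow-up. If the observed difference is near zero, the conclusion is hard to overturn.

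The R.24.1 precedent is also modest. It concerns four European institutions and lists registries as one route among several, whereas up to 75 of the 115 planned centers here are in the United States. It shows that the method is known, not that access is equal everywhere.

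None of this removes the gap in the required steps or the month-60 timing.

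**Conclusion.** The point holds in a limited form. The required tracing does not include a public-record search or a vital-status sweep before the 24-month analysis. Continued contact after loss is left unstated, and the one-time check for withdrawn subjects comes too late for nearly all of them. It would go too far to say that findable deaths will be missing: that is a possible result of following the minimum steps, and the number is unknown.

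The plausible effect is 0.5 to 1.1 points on the difference, under the assumption of 25 to 35% risk among the missing in one arm, 17% in the other, and the full 6% missing in each. It is zero if loss and risk are equal. An effect of this size could matter if the observed difference lies within about a point of the limit near 3.3 points, and would hardly matter if the difference is near zero. I would class the change as a cheap improvement.

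**What to change.** In C.4.19:

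1. State that the vital-status contact described in C.4.15 continues at each visit window after a subject has been deemed lost.
2. Move the one-time vital-status check for consenting withdrawn subjects to month 24, or add one there.
3. Before each Win Look, and in both arms alike, carry out a vital-status sweep of all lost and withdrawn subjects, including a death or civil registry search where law and consent allow.
4. Count registry deaths on or before day 730 as primary endpoint events. Bring registry-confirmed survivors into the primary analysis too, for example as alive with disabling-stroke status carried from last contact or imputed, with a sensitivity analysis on that status.

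The second half of item 4 is essential. Take 752 observed subjects in an arm at 17% (127.8 events) and 48 lost, of whom 30% died (14.4) and none of the survivors had a disabling stroke; these rates are assumptions. The true rate is (127.8 + 14.4) / 800 = 17.8%. Ignoring the lost gives 17.0%. Adding the deaths but leaving the survivors missing gives (127.8 + 14.4) / (752 + 14.4) = 18.6%. An understatement of 0.8 points would become an overstatement of 0.8.

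The SAP should say how outcomes still missing after the sweep enter the primary analysis, and should include a tipping-point analysis, unless it already does.

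The cost is protocol wording, a registry query for at most about 100 subjects, and consent or privacy clearance in some countries, which is the main downside. Sample size, margin and thresholds do not change.
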